#### c. Advertisements

An approved study flier and recruitment brochure will be placed in key places and/or be distributed to physician offices, related clinics, or on other occasions/venues that present as an opportunity to recruit (e.g., a PI speaking engagement or a community outreach event to reach minority subjects). Potential subjects can self-refer by contacting the study staff via a telephone number/email address that is provided on these advertisements. Study staff will utilize the approved phone screening script when responding to interested candidates. With subject permission, they will be screened on the phone to make a preliminary assessment of eligibility. We will obtain permission to access their medical records in the UPMC database or request records from their provider as needed to further document eligibility.

Advertisements, such as on radio, television, or print copy in newspapers, or bus signs, may also be utilized depending on recruitment rates.

- Once subjects have been determined to be eligible from medical record review and attending approval, recruitment and enrollment procedures will then follow, including:
- a) Confirmation of eligibility by study physician.
- b) Setting dates for patient visits will also occur prior to screening visit to maintain timeliness of visits per protocol.

- Sponsor: [name]
- c) Scheduling outpatient screening visit (Visit 1) where study risks and potential benefits and rights as a research subject will be described in detail, informed consent will be obtained, and final eligibility will be confirmed.
- d) To minimize the possibility that subjects will feel obligated to participate, investigators will reinforce with their subjects that participation is voluntary, that they do not have to participate, and that the decision not to participate will not affect their care, now or in the future. The investigator will also allow subjects to make further inquiries if they are interested.

#### 4.2 INFORMED CONSENT PROCEDURES

Informed consent is a process that is initiated prior to the individual's agreeing to participate in the study and continues throughout the individual's study participation. Extensive discussion of risks and possible benefits of participation in this study will be provided to the subjects and their families. Consent forms describing in detail the study procedures and risks are given to the subject and written documentation of informed consent is required prior to enrolling in the study. Consent forms will be IRB approved and the subject will be asked to read and review the document. Upon reviewing the document, the investigator will explain the research study to the subject and answer any questions that may arise. The subjects will sign the informed consent document prior to being enrolled in the study. The subjects should have the opportunity to discuss the study with their surrogates or think about it prior to agreeing to participate. The subjects may withdraw consent at any time throughout the course of the study. A copy of the informed consent document will be given to the subjects for their records. The rights and welfare of the subjects will be protected by emphasizing to them that the quality of their medical care will not be adversely affected if they decline to participate in this study.

Prior to performing any of the research study procedures or interventions, subjects must provide informed consent. The investigator will verbally explain the study to the potential subject in a language understandable to subjects, providing all pertinent information (purpose, procedures, risks, benefits, alternatives to participation, etc.), and will allow potential subjects ample opportunity to ask questions to elicit a better understanding of the study. Following this verbal explanation, potential subjects will be provided with a local IRB approved consent form and will be asked to read and review the document. Upon reviewing the document, the investigator will provide adequate opportunity for the subject to consider all options, and answer any additional questions the potential subject may have. Every effort will be made to ensure that subjects have comprehended the study information prior to obtaining subject's voluntary agreement to participate.

#### Remote Consenting

Remote consenting may be used as opposed to in person consenting where possible to reduce unnecessary in person encounters. In the event remote consenting is utilized, subjects will be provided with a copy of the informed consent prior to the teleconsent meeting either via email, fax, mail or previously provided during an in person visit. After the physician investigator and subject review the consent form via video conferencing (e.g., telephone, conference call, videoconference, telemedicine, etc.), the subject will be offered the opportunity to ask any questions and have those questions answered. The subject will sign and date the informed consent.

The physician investigator will verify the subject physically signed the consent document either by viewing via video conference or obtaining a photo of the complete signed consent signature page or obtaining verbal confirmation from the subject that he/she signed the consent form or agreed to participate electronically. The signed document is then mailed, emailed, photo/scanned to text or faxed to the study team.

If the signed consent is provided as an electronic copy (emailed, photo/scanned, or faxed), the subject will return the original signed document on their first in person visit or by mail. If the signed consent form is mailed to the study team, the physician investigator will sign their copy which they possess after the subject has acknowledged signature on their copy. Once the subject's original copy is received the study team's copy will be attached to make a single document.

The study team will document the remote consent process, including the date and time the conversation occurred, how it occurred (e.g., telephone, video conference), the names of the participants, confirmation that the subject received the informed consent, and confirmation of verbal informed consent to participate.

In addition, older potential participants whose competency to consent is in question will be tested for sufficient comprehension and recall of the information presented. Prospective subjects who do not remember the important facts about participation in the research study after repeated testing will not be included in the study.

The subjects may withdraw consent at any time throughout the course of the study. A copy of the informed consent document will be given to the subjects for their records. The rights and welfare of the subjects will be protected by emphasizing to them that the quality of their medical care will not be adversely affected if they decline to participate in this study.

#### 5. POTENTIAL RISKS AND BENEFITS

## 5.1. Risk of Experimental Drug Intervention

Numerous studies have evaluated acute, subacute, and chronic drinking water exposures of nitrite in laboratory animals, and drinking water and dietary exposures in humans. Recent studies are available using a high dose of nitrite by oral route in the form of beet root juice. Recent studies have evaluated acute exposures of oral preparations of nitrite on PK and blood pressure and are characterized below. More extensive human data is available on parenteral sodium nitrite as it is currently available and approved by the FDA for use in the emergency treatment of cyanide poisoning. [72, 73] It is also notable that neutrapharmaceutical preparations are currently being sold with levels of nitrite (12.7 mg per tablet).

#### Nitrite:

Sodium nitrite has been used commercially as a food preservative, an anti-corrosive agent, a coloring agent, and an anti-anginal agent, with additional uses in laxatives, burn ointments, and liniments. Amyl nitrite has been inhaled or ingested as an euphoric stimulant. Nitrite has also been found as a contaminant in well water. Literature searches generated case reports of nausea, vomiting, abdominal pain, dizziness, headache, flushing, cyanosis, tachypnea, dyspnea, hypotension, and death attributed to excess nitrite (high-dose) exposure from these sources as a consequence of methemoglobinemia due to oxidation of heme-iron in oxyhemoglobin. Normal background methemoglobin production is 1-3%. If levels of methemoglobin rise above approximately 30% of total hemoglobin, a subject may appear cyanotic and experience dyspnea, due to the reduced oxygen carrying capacity of hemoglobin

(methemoglobin cannot bind oxygen). Levels above 50% can cause seizures, hypotension, coma, and death. Sodium nitrite administration for cyanide poisoning at the labeled dosage of 300 mg causes methemoglobinemia, a desirable effect, as methemoglobin binds to cyanide, thus protecting cellular mitochondria. A standard dose of nitrite used for cyanide poisoning is 300 mg up to 600 mg. Note that methemoglobin levels have never risen higher than 3% at the currently used therapeutic doses (< 75 mg) in 80 volunteers in phase I studies at the NIH.

The Sponsor of this study proposal, [name], has previously held an IND for sodium nitrite (IND # 70,411) for cardiovascular applications and currently has an approved IND for the use of sodium nitrite for lung transplant recipients (IND # 111,643). The cardiovascular IND involved the administration of sodium nitrite to 69 normal volunteers in 4 phase I-II clinical trials without observed adverse effects. He has also treated 11 subjects with sickle cell disease on this IND without observed adverse effects. The lower doses of nitrite used in these investigational treatment regimens – 60-120 mg daily or 20-40% of the dose (300mg) used in the emergency treatment of cyanide poisoning – do not produce methemoglobin levels greater than 3% and have not been associated with clinically significant hypotension. There have been no adverse events noted in the 80 treated normal human volunteers and patients with sickle cell disease. In another study by [name] et al., 18 healthy adults received an infusion of sodium nitrite totaling 75 mg (15 minutes each x 2 infusions). This was associated with a 7 mmHg decrease in mean arterial pressure, a peak methemoglobin of less 3%, and no other significant effects. Note this single dose is 1.9 times the single dose per time of day we plan to use in this trial.

In an open-label three-way crossover study, 9 healthy adult subjects received two single high dose oral sodium nitrite aqueous solutions (0.12 and 0.06 mmol NaNo2/mmol Hb, equivalent to 290-380 mg and 140-190 mg sodium nitrite, respectively, depending on the total body hemoglobin level of the person) and one intravenous sodium nitrite dose (0.12 mmol NaNo2/mmol Hb). Note that this is 1.2-3.2 times the daily dose we plan to use in this trial. There was a washout period of at least 7 days between each of the treatments. Mild headache occurred in 44-55% of subjects and was the most frequent complaint during each treatment session, which the authors ascribed to the sodium nitrite, not methemoglobinemia, as the percentage of methemoglobinemia stayed below clinically toxic levels (<15%). By report, up to 22% experienced nausea, which subsided within half an hour. The pharmacokinetic analysis of this study indicated similar bioavailability of oral and IV delivery of nitrite, as well as similar side effect and safety profiles.

A recent study determined the safety and feasibility of prolonged intravenous nitrite infusion. Twelve adult volunteers received increasing starting doses of sodium nitrite, 4.2 to 533.8 µg/kg/hr for 48 hours. Dose limiting toxicity occurred at 445.7 µg/kg/hr (10.6 mg/kg/day) and was limited to asymptomatic transient decreases of arterial blood pressure of up to 20 mmHg and asymptomatic increases of methemoglobin levels above 5%. No tolerance or clinically significant rebound was observed. Note, this is 8.2 times the daily dose we plan to use in this trial (based on an adult body weight of 95 kg).

For nitrite, two retrospective case-control studies have shown that high maternal dietary nitrite intake from cured meat or drinking water during pregnancy might be associated with risk of childhood brain tumors and possibly gastric and esophageal cancer. This evidence is only based on retrospective case-control studies; cohort studies have found no significantly increased risks.

In the 2001 National Toxicology Program (NTP) Report summarizing 2-year rodent drinking water studies, there was no evidence of carcinogenic activity of sodium nitrite in male or

female F344/N rats exposed to up to 130 mg/kg/day in males and 150 mg/kg/day in females, or in male B6C3F1 mice exposed to up to 220 mg/kg/day. There was equivocal evidence of carcinogenic activity of sodium nitrite in the highest dose of 165 mg/kg/day in female B6C3F1 mice based on the positive trend in the incidences of squamous cell papilloma or carcinoma (combined) of the forestomach. Exposure to sodium nitrite in drinking water resulted in increased incidences of epithelial hyperplasia in the forestomach. However, no chromosomal damage (genetic toxicity) was observed in three studies conducted in rats and mice *in vivo*. Taken together, these findings suggest minimal carcinogenic nitrite-mediated risk.

In the current study, we will use lower doses of nitrite than used safely in any of these studies. Our nitrite dose of 40 mg three times daily is lower than the dose used on the cardiovascular IND and < 40% of the dose for cyanide poisoning.

To summarize, we anticipate the following symptoms by organ system and likely frequency of risk:

#### Gastrointestinal

Common: noneFrequent: none

Infrequent: dry mouth

Rare: nausea, abdominal pain, and vomiting

## Hematologic

Common: noneFrequent: none

Rare: methemoglobinemia

#### Cardiovascular

Common: noneFrequent: none

• Rare: flushing, tachycardia, hypotension

## Neurologic

Common: noneFrequent: none

Rare: headache, dizziness, seizure, coma

#### Respiratory

Common: noneFrequent: none

• Rare: tachypnea, dyspnea, cyanosis

#### 5.2 Risk of Study Procedures

#### Risks of Blood Drawing

The amount of blood to be drawn over the course of this research study could be a maximum of 40 tablespoons. To minimize the risks of blood tests, all blood draws are performed by trained RN, MD, technician or phlebotomist.

Common risks include temporary discomfort, bruising which may last for several days, redness, swelling, lower hemoglobin level. Infrequent risks include a subject may feel

lightheaded or faint when blood is drawn. This is usually due to nervousness and is not usually serious. Rare risks include infection and bleeding.

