#### 2.3.1. Screening Procedures

The outpatient visits will take place in various outpatient clinics and/or procedural areas throughout the University of Pittsburgh Medical Center (UPMC) Presbyterian and UPMC Montefiore Hospitals. The screening procedures will take place over 2 days if screening RHC is needed. Subjects will be asked to fast a minimum of 8 hours prior to each visit. These screening procedures will determine eligibility for the study.

- Obtain written informed consent
- Complete history and physical examination to include body weight, height
- Vital signs that include: blood pressure (BP), pulse, respirations, and pulse oximetry
- Obtain waist measurement
- Review of concomitant medications
- NYHA functional class assessment
- 6 minute walk test (6MWT) and Borg scale
- MetHb level via co-oximetry (pre single dose and 30 minutes post single dose). Due
  to unknown reasons the co-oximeter device may not be able to read metHb levels. In
  that event, a blood sample will be collected to test metHb levels at approximately 3045 minutes after the 40mg dose.
- Blood samples: fasting glucose, comprehensive metabolic panel, hemoglobin A1C, fasting lipid profile, PT/PTT, complete blood count, platelet and differential, NT-proBNP. The total volume of blood drawn is approximately 1 ½ tablespoons (20 mL). If any of the above tests were done within 30 days before the screening visit, they may or may not be repeated for research purposes.
- Urine pregnancy test for women of childbearing potential
- Echocardiogram (if subject has had an echocardiogram within the past year we may not obtain during screening)
- Right heart catheterization (with optional micromanometry), research blood samples
  for plasma nitrite concentrations, red cell iron-nitrosyl-hemoglobin and platelet studies,
  and open label 40mg oral nitrite dosing with methemoglobin level. Research blood
  samples will be collected prior to taking the 40mg oral nitrite and approximately
  30-45 minutes post-dose.
- A RHC may be performed to determine the PH-HFpEF eligibility criteria. The RHC will be conducted at UPMC Presbyterian Hospital, 3rd FL Catheterization Laboratory. The RHC hemodynamic measurement parameters for PH-HFpEF eligibility are as follows: mPAP ≥ 25 mm Hg; PCWP ≥15 and TPG ≥ 12. If a RHC has been completed within 12 months from enrollment, test results may be considered for baseline measurements. The total volume of blood drawn is approximately 1 ¾ tablespoons

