#### Clinic Visit Week 10 (+/- 14) and End of Treatment (+/- 14) to begin testing visits)

These visits may take up to 4 days to complete all the assessments. Subjects e instructed to arrive in a fasted state and hold study medication the morning of these scheduled visits. Participants will take their morning or afternoon dose under direct supervision of the study team and will continue to take the study medication TID until all testing is completed.

- Self-administration of drug by subject under direct supervision of study team at the start of each visit
- Interval history
- Physical examination including vital signs, pulse co-oximetry, and body weight
- Waist measurement
- Methemoglobin percentage level via co-oximetry (approximately 30-45 minutes post study medication)
- Review of concomitant medications
- Collection of used study drug and diary; review for compliancy and symptoms
- Functional Class assessment
- 6MWT and Borg scale
- Accelerometer
- Urine pregnancy if applicable
- Echocardiogram

- Sponsor: [name]
- Blood samples: fasting glucose, comprehensive metabolic panel, hemoglobin A1C, fasting lipid profile, PT/PTT, complete blood count, platelet and differential, and NT-proBNP. The total volume of blood drawn for these samples is approximately 1 ½ tablespoons (20 mL).
- Cardiopulmonary exercise test (CPET): Constant Work Rate Test
- RHC: Hemodynamic measurements will be completed at rest. Once the resting measurements are completed, the patient will take a single dose of their randomly assigned study medication. Another set of hemodynamic measurements will be taken approximately 30-45 minutes after the study medication is taken. Following these measurements, the patient will complete a constant workrate supine exercise test lasting about 4-12 minutes. Patients will pedal until exhaustion. The information collected from the baseline constant workrate exercise test during the baseline procedures will determine the watts used for the constant workrate supine exercise tests in the catheterization lab during weeks 10 and EOT. Hemodynamic measurements will be taken about every 2 minutes during the exercise test.
- Micromanometry (optional) during RHC
- Research blood samples (plasma nitrite concentrations, red cell iron-nitrosyl-hemoglobin, and platelet studies) during RHC: pre-dose and approximately 30-45 minutes post dosing of study drug. The total volume of blood drawn is approximately 1 /4 tablespoons (26 mL).

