## **Cross-Over Visit**

This visit may be completed over 2 days dependent on patient and staff availability. Subjects will be instructed to fast for a minimum of 8 hours on the day of the bloodwork. Patients will only need to fast for 2 hours prior to the constant work rate exercise test.

- Self-administration of drug by subject under direct supervision of study team
- Interval history
- Collection of diary; review for compliancy and symptoms
- Physical examination including vital signs, pulse co-oximetry, and body weight
- Urine pregnancy if applicable
- Methemoglobin percentage level via co-oximetry (approximately 30-45 minutes post study medication)
- Review of concomitant medications
- Functional Class assessment
- 6MWT and Borg scale
- Constant work rate exercise test
- Accelerometer

- Sponsor: [name]
- Blood samples: fasting glucose, comprehensive metabolic panel, hemoglobin A1C, fasting lipid profile, PT/PTT, complete blood count, platelet and differential, NT-proBNP, research blood samples: plasma nitrite concentration, red cell iron-nitrosyl-hemoglobin, and platelet studies. The total volume of blood drawn for these samples is approximately 2 ½ tablespoons (35 mL).
- Dispense study drug and diary cards
- AE/SAE assessment
- Completion of the KCCQ, SF-36 and PAH-SYMPACT Questionnaires

Weekly phone follow-up (+/- 7 days) assessments will occur while on active study treatment (when subjects are not followed up in clinic) that will include symptom review, assessment of adverse events, review of concomitmant medications, and interval histories. Subjects will return to clinic at week 10 and undergo study procedures as noted in the first 10 weeks.

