## 2.4.9 Intravenous Glucose Tolerance Test (IVGTT)

This visit will take place in the Montefiore CTRC. This test will occur at least 48 hours after the last exercise bout to account for the effects of acute exercise on insulin resistance. Subjects will be asked not to drink or eat anything other than plain water for 8 hours prior to their arrival for this visit.

Both glucose and insulin will be injected intravenously into the arm. Blood samples will be taken over the course of 3.5 hours, totaling about 15 1/2 tablespoons.

The IVGTT is considered a gold-standard test to measure insulin secretion and sensitivity. It has been standardized and used worldwide for more than 20 years. In our study, the expected duration is 180 mins after the test is started with an IV glucose bolus of 0.3g/kg. After the glucose bolus, a small dose of human regular insulin is given IV to moderate the plasma glucose rise. The insulin dose is 25 mUnits/Kg body weight. Patients taking oral hypoglycemics may be asked to hold those medications the morning of the IVGTT but can resume taking them following the completion of the IVGTT the same day.

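### The stated maximum of 40 tablespoons of blood appears to leave out the screening draws, so it is about 7-8% too low for a patient who has them all and both optional IVGTTs

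*Combined protocol and SAP*

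**What the plan says.** Section 5.2 (Risks of Blood Drawing) gives one total for the whole study, saying that the amount drawn "could be a maximum of 40 tablespoons". The same paragraph names a lower hemoglobin level among the common risks.

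The component volumes are spread over Section 2:

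- **Screening (2.3.1).** The laboratory panel takes 1 ½ tbsp (20 mL). For the right heart catheterization (RHC) research samples, "The total volume of blood drawn is approximately 1 ¾ tablespoons" (26 mL). Recent laboratory results can stand in for new ones: "If any of the above tests were done within 30 days before the screening visit, they may or may not be repeated for research purposes". An RHC done within 12 months of enrollment can replace the screening RHC.
- **Week 10 and EOT (2.3.3).** Each visit has a panel of 1 ½ tbsp (20 mL), RHC research samples of 1 ¾ tbsp (26 mL) and an optional IVGTT.
- **IVGTT (2.4.9).** "Blood samples will be taken over the course of 3.5 hours, totaling about 15 1/2 tablespoons". A footnote to Table 1 excludes insulin-dependent diabetics from this test.
- **Cross-over visit (2.3.3).** 2 ½ tbsp (35 mL).
- **Weeks 4 and 8 of each arm (2.3.3).** 1 teaspoon for NT-proBNP, only if the investigator calls the patient in.
- **Open-label period (2.3.5).** 4 mL for NT-proBNP, collected at months 3 and 6. The text does not say whether 4 mL is per visit or in all.
- **Backup methemoglobin samples (2.3.1 and 2.4.7).** Drawn if the co-oximeter cannot give a reading. No volume is stated.

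**The concern.** A figure described as a maximum should cover the patient who has everything the protocol provides for. Adding the protocol's own volumes for that patient gives more than 40 tbsp.

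What is at stake is the accuracy of a disclosed risk. Eligibility admits patients with hemoglobin down to 9 g/dL, and the protocol itself lists a fall in hemoglobin as a common effect of the blood draws, so the total should agree with the schedule. The endpoints, sample size and analysis do not depend on it.

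**Working it through.** **Inputs, in tablespoons as printed**

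| Draw | Volume | Times | Source |
|---|---|---|---|
| Screening panel | 1.5 | 1 | 2.3.1 |
| Screening RHC samples | 1.75 | 1 | 2.3.1 |
| Week 10 / EOT panel | 1.5 | 2 | 2.3.3 |
| Week 10 / EOT RHC samples | 1.75 | 2 | 2.3.3 |
| IVGTT | 15.5 | 2 | 2.4.9, Table 1 |
| Cross-over visit | 2.5 | 1 | 2.3.3 |

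**Step 1: reproduce the plan's figure.** Week 10 is 1.5 + 1.75 + 15.5 = 18.75 tbsp, and EOT is the same. With cross-over, 18.75 + 2.5 + 18.75 = 40.00 tbsp. This is the stated maximum exactly, and it contains no screening draw.

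**Step 2: add screening.** 1.5 + 1.75 = 3.25 tbsp, so the total is 40.00 + 3.25 = 43.25 tbsp. The excess is 3.25 / 40 = 8.1%.

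**Step 3: repeat with the printed millilitres.** The protocol gives no millilitre figure for the IVGTT, so I assume 14.787 mL per tablespoon.

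- Panels and RHC samples: 3 x (20 + 26) = 138 mL
- Cross-over: 35 mL
- Two IVGTTs: 2 x 15.5 x 14.787 = 458 mL
- Total: 631 mL, which is 631 / 14.787 = 42.7 tbsp
- Stated maximum: 40 x 14.787 = 591 mL

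The excess is about 40 mL, or 7%. At 15 mL per tablespoon the comparison is 638 mL against 600 mL, an excess of about 6%.

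**Step 4: vary what the patient has.**

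| Patient | tbsp as printed | tbsp from printed mL |
|---|---|---|
| All screening draws, two IVGTTs | 43.25 | 42.7 |
| Screening RHC samples only, two IVGTTs | 41.75 | 41.4 |
| Screening panel only, two IVGTTs | 41.50 | 40.9 |
| No screening draws, two IVGTTs | 40.00 | 39.6 |
| All screening draws, one IVGTT | 27.75 | 27.2 |
| All screening draws, no IVGTT | 12.25 | 11.7 |

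**Step 5: add the discretionary draws to the 43.25 tbsp.** Four week 4/8 clinic visits at 1 teaspoon (1/3 tbsp) add 1.33 tbsp, giving 44.58. Open-label NT-proBNP adds 4 mL (0.27 tbsp) if that is the total, or 8 mL (0.54 tbsp) if it is per visit, giving 44.85 or 45.12. Backup methemoglobin samples would come on top.

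**Step 6: check that the full-schedule patient is foreseen.** Section 7.2 pays $1,400 when all study procedures are completed. That sum is $200 (baseline visits with screening RHC) + $400 (week 10, with IVGTT) + $50 (cross-over) + $750 (EOT, with IVGTT). The protocol's own complete patient therefore has the screening RHC and both IVGTTs.

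**The case against.** The strongest reply is that most patients may never approach the figure. The IVGTT is optional, is not done in insulin-dependent diabetics, and supplies 31 of the 43.25 tbsp. The screening panel and the screening RHC can each be waived; without either, and without discretionary draws, the total is 40.00 tbsp. This stands, and it limits the point to patients who have both IVGTTs and at least one screening or discretionary draw. It does not rescue a stated maximum, which has to cover the patient with the most draws.

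A second reply is that the volumes are approximate and some tablespoon figures are rounded up: 20 mL is 1.35 tbsp, printed as 1 ½. This also stands, and it is why the millilitre total is lower. But that total still exceeds 40 tbsp, and the gap in printed tablespoons equals the screening draws exactly. An omitted visit explains it better than rounding does.

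A third reply is that 15.5 tbsp might cover both IVGTTs, which would bring the full total down to 27.75 tbsp. Section 2.4.9 describes sampling over 3.5 hours, which is one test, and 40.00 is recovered only when 15.5 is counted twice.

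A reader might also infer that 40 tbsp is an operating limit which the schedule breaches. The documents do not support that. Section 5.2 is descriptive risk text, and no eligibility, withdrawal or stopping rule refers to the figure.

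**Conclusion.** The stated maximum is understated for a patient profile that the protocol itself foresees. With all screening draws and both IVGTTs the total is about 43.25 tbsp by the printed tablespoons, or about 631 mL (42.7 tbsp) by the printed millilitres. That is roughly 7-8% over, or some 40-50 mL. With the discretionary and open-label draws it reaches about 45 tbsp, plus backup methemoglobin samples.

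This rests on two assumptions: that 15.5 tbsp is the volume of one IVGTT, and that a tablespoon is 14.787 mL. That screening was left out is inferred from the exact match at 40.00; the protocol does not show how the figure was built.

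A reader might infer that every patient who follows the schedule exceeds 40 tbsp. That does not follow: with one IVGTT or none the total is far below it. The point is minor. It concerns the accuracy of a risk statement and affects no trial result.

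**What to change.** Reconcile the maximum in Section 5.2 with the visit-level volumes. Restate it to include the screening, investigator-requested, backup methemoglobin and open-label draws: about 45 tbsp plus the backup samples, whose volume should be given. While doing so, say whether the open-label 4 mL is per visit or in total. A note that the total depends mainly on whether the optional IVGTTs are done would help the reader.

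Align any participant-facing text that repeats the figure. The consent form is not part of the text reviewed, so whether it needs the change has to be checked.

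The cost is wording only, and the disclosed volume becomes slightly less favourable. No procedure, visit or analysis changes.
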